#### 6.0 Data and Specimen Banking

6.1 Storage and Access: Urine will be collected from subjects at the Day 1 and Weeks 1,2 and 4 visits. The samples will be stored in freezers located in labs used by faculty in the ECP department (currently these freezers are located on the 5th floor of [name]). Samples will be stored until later batch analysis can be completed.

# 7.0 Sharing of Results with Participants

7.1 Study results will not be shared with participants.

## 8.0 Study Duration

- The anticipated duration for an individual participant's participation in the study is approximately 6 weeks (depending in part on length of time between the screening visit and first tDCS visit).
- Data collection is expected to be complete within 1 year of starting the study.

## 9.0 Study Population

- **9.1** Inclusion Criteria: To be eligible subjects must:
  - a) Be between the ages of 18 and 64
  - b) Smoke (on average) at least 5 cigarette per day
  - c) Be motivated to quit smoking
- **9.2** Exclusion Criteria: Subjects will be excluded if they:
  - a) Regularly use tobacco products other than cigarettes (> 9 times per month)
  - b) Have any major medical or psychiatric condition that is unstable and renders them unable to participate in the study.
  - c) Have any medical condition with neurological sequelae (e.g., stroke, seizures).
  - d) History of loss of consciousness of greater than 30 minutes duration or loss of consciousness with neurological sequelae
  - e) Have any medical condition or use any medication that would either increase risk of subjects participating in this study (e.g., medications that lower the seizure threshold) or that would impact measures of interest (e.g. smoking cessation medications).
  - f) Have any contraindications for MRI scanning (e.g., metal implants, pacemakers or any other implanted electrical device, injury with metal, braces, non-removable body piercings, pregnancy)
  - g) Are pregnant or planning to become pregnant during the study
  - h) Have any contraindications to tDCS (e.g., current use of pacemaker, intracranial electrodes or implanted defibrillator).
- 9.3 Screening: At the screening visit, subjects will complete a serious of questionnaires including those that ask about medical history, smoking history and motivation to quit smoking. All inclusion / exclusion will be based on self-report except for smoking status which will be confirmed via an exhaled carbon monoxide (CO) concentration of ≥ 8 ppm or a urinary nicotine test strip reading of 6. Non-pregnant status will be confirmed via a urine pregnancy test.

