## 3.0 Study Endpoints/Events/Outcomes

- **3.1** Primary Endpoint/Event/Outcome: As a pilot study, the main objective of this investigation is to determine the feasibility of using the proposed approach as a method by which to increase smoking cessation rates. The primary endpoint is therefore to determine if recruiting smokers into a study evaluating tDCS will be feasible and if the intervention is well tolerated by smokers.
- 3.2 Secondary Endpoint(s)/Event(s)/Outcome(s): Secondary endpoints include measures associated with smoking cessation outcomes including time to smoking lapse, time to smoking relapse, number of cigarette smoked, severity of craving and severity of withdrawal symptom score. We will also assess impulsivity as tDCS may impact this measure. fMRI measures will be assessed in the subpopulation of subjects enrolled after protocol revision # 3 is approved and after all preparations to enroll subjects into this portion of the study are complete.

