#### 5.0 Procedures Involved

- **5.1** Study Design: This study is a randomized double-blind pilot study in which subjects will receive either active or sham tDCS
- **5.2** Study Procedures: The following procedures will occur during the study
- 5.2.1 Screening visit: Initial eligibility will be assessed via a phone interview. Those likely to qualify will be scheduled for a screening visit at which written informed consent will be obtained and eligibility confirmed. Medical, psychiatric and smoking history will be obtained via subject report with smoking status biochemically confirmed (via an exhaled carbon monoxide (CO) concentration of > 8 ppm or a urinary nicotine test strip = 6). Baseline levels of a variety of measures such as severity of smoking urges, severity of withdrawal symptoms, extent of nicotine dependence and how subjects evaluate their current cigarettes will be assessed via questionnaires. Height and weight will be measured. Those who qualify will be scheduled for a week during which they will come in daily for 5 consecutive days to receive tDCS treatments (active or sham) and will be asked to maintain a daily tobacco use diary in order to assess baseline levels of smoking. Subjects enrolled after revision # 3 has been approved and all preparations to enroll subjects into the scanning portion of the study are complete will be asked to come in for two additional visits to collect fMRI data: one visit before tDCS treatments begin, and a second visit after all tDCS treatments are completed.
- 5.2.2 MRI scanning visits (2 visits, 1 visit occurring during the week prior to and the other visit occurring during the week following the tDCS visits): Participants will undergo an MRI scan (3T), which takes about 75 to 80 minutes. MRI involves taking pictures of the participant's brain, from which the properties of certain brain tissues can be measured. These scans are strictly for research

purposes and therefore will not receive a clinical or medical interpretation. For the scan, the participant will be asked to lie down quietly on a bed, and the bed will slide into the scanner. Once the participant is inside the scanner, the imaging will begin. During the scan, the participant will be asked to lie quietly in the scanner with their eyes closed and may also be asked to perform a cognitive task (e.g., reversal learning task). The MRI scan will be performed at the University of Minnesota's Center for Magnet Resonance Research.

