At the beginning of each tDCS visit, participants will be assessed for number of cigarettes smoked 24 hours prior to the session, the time since last cigarette and exhaled CO levels. A cigarette evaluation scale will be completed at each visit. Additionally, adverse events, smoking urges and nicotine withdrawal symptom severity will be assessed before and after each session using several questionnaires. At the first tDCS session, urine will be collected to be analyzed at a later time for markers of cigarette smoking (e.g., cotinine concentrations). Prior to the first and after the last tDCS session, participants will also complete an impulsiveness questionnaire as this parameter is thought to be affected by tDCS, a

questionnaire assessing nicotine dependence as well as a questionnaire assessing motivation and self-efficacy to quit smoking.  Total participation time at each visit is not expected to exceed 2 hours per day.

At these visits, participants will be provided a smoking cessation treatment manual (Clearing the Air) and begin preparation for the quit date, which will be at the end of the 5th visit. The standardized content of the brief (10 min) behavioral treatment session provided to participants will include discussing benefits of quitting, ways to prepare the environment to minimize smoking cues (e.g., removing ashtrays), and methods to reduce craving and withdrawal symptoms (e.g., deep breathing). Participants will also keep track of situations associated with smoking and begin to develop a plan to deal with these situations.

This tDCS device to be used in this study is located in the MnDRIVE Non-invasive Neuromodulation Laboratory. There is currently no evidence of serious side-effects.  Mild side-effects that typically resolve upon discontinuing tDC include light itching under the electrode at the beginning of administration, headache, fatigue, and nausea. The subject may choose to discontinue stimulation at any time during the session if experiencing excessive discomfort or side effects. Although seizures are not a known risk of tDCS intervention,  anyone with a history or a risk for seizures will be excluded from the study. No other risks related to tDCS are anticipated.

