- **14.2** Reproduction Risks: There is limited data regarding the risks of tDCS to an embryo or fetus although since tDCS is a localized brain stimulation treatment, it is unlikely to have reproductive risks. The risks of MRI to fetuses are unknown. We will therefore exclude women who are pregnant or are planning to become pregnant during the study.
- **14.3** Risks to Others: There are no anticipated risks to others.

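### The only pregnancy test written in the protocol is at screening; none is written before either MRI scan, although Section 14.2 treats fetal MRI risk as unknown

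*Combined protocol and SAP*

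**What the plan says.** Section 9.3 (Screening) sets the general rule for eligibility: "All inclusion / exclusion will be based on self-report except for smoking status". It then adds one laboratory check for pregnancy: "Non-pregnant status will be confirmed via a urine pregnancy test". No other pregnancy test is written. The MRI visits (5.2.2), the tDCS visits (5.2.3) and the follow-up visits (5.2.4) list none.

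Pregnancy appears in two exclusions: 9.2(f), as an MRI contraindication, and 9.2(g), which also covers women planning pregnancy during the study. Section 14.2 gives the reason. For MRI, "The risks of MRI to fetuses are unknown"; for tDCS, "it is unlikely to have reproductive risks". It concludes: "We will therefore exclude women who are pregnant or are planning to become pregnant during the study".

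Section 5.2.2 times the two scans as "1 visit occurring during the week prior to and the other visit occurring during the week following the tDCS visits". Scanning covers only part of the sample. Section 3.2 says: "fMRI measures will be assessed in the subpopulation of subjects enrolled after protocol revision # 3 is approved".

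Section 14.1 describes further MRI safeguards: a contraindication questionnaire reviewed by imaging-centre staff, a decision on whether the subject may be scanned, and screening of everyone before they enter the magnet area.

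**The concern.** The protocol does not leave pregnancy to self-report alone; it adds a urine test. But it applies that test only once, at screening, and scan 2 comes after the whole tDCS block. A woman who conceived shortly before or after screening could test negative there, not know that she is pregnant, and be scanned. Excluding women who plan a pregnancy does not deal with an unplanned one, and a questionnaire cannot report what the respondent does not know.

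At stake is a fetal exposure whose risk the protocol calls unknown, from a scan done only for research, in a study that 15.1 says offers participants no direct benefit. The point concerns only women who could be pregnant and who are in the imaging part. It concerns safety only and does not touch the feasibility endpoint or the analyses in 16.0.

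**Working it through.** The protocol does not state the interval from test to scan, so it has to be built from the visit schedule.

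**Inputs**
- Screening, with the urine test: day 0 (9.3).
- First tDCS visit: day g. Section 8.0 says that total duration depends partly on this gap and sets no limit on it.
- tDCS: 5 consecutive days (5.2.3), so the fifth visit is day g+4.
- Quit date, in the plan's words: "begin preparation for the quit date, which will be at the end of the 5th visit". This is also day g+4.
- Follow-up: 4 weekly visits (5.2.4), so the last is day g+4+28 = g+32.
- Scan 1 in the week before tDCS: days g−7 to g−1, and not before day 0.
- Scan 2 in the week after tDCS, read as 1 to 7 days after the fifth visit: days g+5 to g+11.

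**Reproducing the plan's own figure.** Section 8.0 gives about 6 weeks per participant. Setting g+32 = 42 days gives g = 10, exactly 6.0 weeks. With g = 7 the total is 39 days, or 39/7 = 5.6 weeks. Both fit the stated duration.

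**Interval from the only test to each scan**

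| g (days) | Total | Scan 1 (days after test) | Scan 2 (days after test) |
|---|---|---|---|
| 2 | 34 days (4.9 weeks) | 0 to 1 | 7 to 13 |
| 7 | 39 days (5.6 weeks) | 0 to 6 | 12 to 18 |
| 10 | 42 days (6.0 weeks) | 3 to 9 | 15 to 21 |
| 14 | 46 days (6.6 weeks) | 7 to 13 | 19 to 25 |
| 21 | 53 days (7.6 weeks) | 14 to 20 | 26 to 32 |

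For g = 7 to 10, scan 1 is 0 to 9 days and scan 2 is 12 to 21 days after the test. The other rows show how far this moves if g differs. Even at g = 0, scan 2 would be at least 5 days after the test.

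**What a scan-day strip gains.** Suppose the assay turns positive L days after conception. The screening test then detects conceptions up to day −L, and a strip on day d detects them up to day d−L. The difference is (d−L) − (−L) = d days, whatever L is. For g = 7 to 10 the gain is therefore 0 to 9 days of detectable conceptions at scan 1 and 12 to 21 days at scan 2. These are upper limits, because self-report would catch some of the same pregnancies. Conceptions in the last L days before the scan still go undetected.

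**Expected number of cases.** This cannot be calculated. The documents give no sex split, number scanned or pregnancy rate. With about 20 completers (11.1), of whom only some are scanned, it must be very small.

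**The case against.** The strongest reply is that pregnancy is already well covered. It is an exclusion and a named MRI contraindication, women planning pregnancy are excluded, non-pregnancy is tested at screening, imaging-centre staff review a questionnaire and approve each subject, and people are screened again before entering the magnet area. What remains is an unrecognised early pregnancy in a woman who tested negative and was not planning to conceive. This is fair and sets the size of the point, but it does not remove it. None of the steps in 14.1 is described as a pregnancy test. The questionnaire is not said to be repeated before scan 2, and the entry screening is described in the context of magnetic objects.

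A second reply is that the imaging centre reviewed the study under its own application (5.5) and may test on the day of the scan. That also stands. Its procedures are not in the documents, so a reader who infers that women would be scanned untested goes too far. What is shown is that the protocol does not write a retest.

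Two other stronger readings should be resisted. The 12 to 21 days might be taken for a protocol figure, but it depends on an assumed g of 7 to 10 days. The gap might also be thought to call for a retest before tDCS, but 14.2 regards that exposure as unlikely to carry reproductive risk, and some subjects receive sham.

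**Conclusion.** The point holds as a minor, safety-only improvement. The protocol writes one pregnancy test, at screening, and none before either scan, while its own exclusion rests on an unknown fetal risk from MRI. Scan 2 falls g+5 to g+11 days after that test, or 12 to 21 days if screening is 7 to 10 days before the first tDCS visit. This rests on that assumed gap and on reading the week after tDCS as days 1 to 7 after the fifth visit. That no retest is written does not depend on either. The plan contains no contradiction here: 14.2 promises an exclusion and 9.3 tests for it. The expected number of cases is very small and cannot be estimated, and the imaging centre may already test.

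**What to change.** In 5.2.2, for women who could be pregnant, add a urine pregnancy strip read before each MRI scan, with no scan if it is positive. Scan 2 is the priority. The strip at scan 1 can be waived if the screening test was done the same day. If the imaging centre already tests on the scan day, one sentence citing that step is enough.

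The cost is at most two strips and a spot urine at the scan visits for each scanned woman. If all 20 completers were scanned women who could be pregnant, that would be 20 × 2 = 40 strips; the true number will be lower. Sample size, endpoints and analyses stay as they are.

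Reusing the urine collected at the Week 1 visit by scanning on that day may look economical, but I would not do it. That visit is day g+4+7 = g+11, the last day of the scan 2 window and a full week after stimulation and the quit date. A slip of one day would miss the window, and smoking status by then may differ between subjects in ways that affect the fMRI measure.

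The retest narrows the undetected window without closing it, because the assay lag remains. A positive strip at scan 2 prevents only that scan, since tDCS is already finished.

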#### **10.0** Vulnerable Populations

Vulnerable Populations:
☐ Children
☐ Pregnant women/Fetuses/Neonates
☐ Prisoners
☐ Adults lacking capacity to consent and/or adults with diminished capacity to consent, including, but not limited to, those with acute medical conditions, psychiatric disorders, neurologic disorders, developmental disorders, and behavioral disorders
☐ Approached for participation in research during a stressful situation such as emergency room setting, childbirth (labor), etc.
☐ Disadvantaged in the distribution of social goods and services such as income, housing, or healthcare
☐ Serious health condition for which there are no satisfactory standard treatments
☐ Fear of negative consequences for not participating in the research (e.g. institutionalization, deportation, disclosure of stigmatizing behavior)
☐ Any other circumstance/dynamic that could increase vulnerability to coercion or exploitation that might influence consent to research or decision to continue in research
☐ Undervalued or disenfranchised social group
☐ Members of the military
☐ Non-English speakers
☐ Those unable to read (illiterate)
☐ Employees of the researcher
☐ Students of the researcher
⊠ None of the above

# 11.0 Local Number of Participants

11.1 Local Number of Participants to be Consented: We plan on recruiting subjects until approximately 20 have completed the study. We expect that as many as 50 subjects will undergo the consent process. Some of those that attend the screening visit will likely not meet inclusion / exclusion criteria whereas others will not be interested in participating.

#### 12.0 Local Recruitment Methods

12.1 Recruitment Process: Advertisements for the study will be placed invarious print and on-line sources and via flyers. Interested participants will call the phone number listed. Study staff will explain the study to potential study subjects. Individuals that indicate an interest in participating in the study will then be screened by telephone to see if they are likely to qualify for the study. Additionally subjects that in previous studies agreed to be contacted regarding other research opportunities may be called – in this case, subjects

will be informed why they are being called with the telephone screening process being the same as for subjects who contacted us after seeing the study advertised.

- 12.2 Recruitment Materials: Flyers and advertisements placed in local publications or on on-line resources (for example, Craigslist) will be used to recruit participants.
- 12.3 Payment: Subjects will receive \$20 for each visit that they complete (e.g. screening visit, MRI scans, 5 visits at which tDCS will be administered, 4 follow-up visits). Subjects who attend all study visits and comply with all study related procedures will receive a \$60 bonus. Subjects can therefore receive up to \$300 for completing the entire study. Payment will be provided at the end of each visit in the form of a pre-paid debit card.

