#### 13.0 Withdrawal of Participants

- 13.1 Withdrawal Circumstances: Participants will be withdrawn from the study if they report any side effects of greater than moderate severity or that raise any safety concerns. Subjects may also be withdrawn from the study if they fail to follow study procedures (e.g., show up to scheduled study visits). Additionally, subjects will be told that participation is voluntary and that they may discontinue participation at any time for any reasons.
- 13.2 Withdrawal Procedures: Subjects who withdraw from the study after having received tDCS will be asked if they can be contacted by telephone to ascertain smoking status. We will attempt to contact subjects by telephone who do not show up to scheduled visit to ascertain if they wish to continue to participate in the study (and if not, why not) and to determine smoking status.

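### Sections 12.3 and 13.1 together give subjects a financial reason to under-report side effects above moderate severity, and 12.3 does not say how a stopped session is paid

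*Combined protocol and SAP*

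**What the plan says.** - **Payment (12.3).** Subjects receive $20 "for each visit that they complete (e.g. screening visit, MRI scans, 5 visits at which tDCS will be administered, 4 follow-up visits"). The bonus rule reads "Subjects who attend all study visits and comply with all study related procedures will receive a" $60 bonus. The section then gives the total: "Subjects can therefore receive up to" $300. On timing: "Payment will be provided at the end of each visit in the form of a pre-paid debit card". It does not mention side effects, withdrawal or stopped stimulation.
- **Withdrawal (13.1).** "Participants will be withdrawn from the study if they report any side effects of greater than moderate severity", or if the effect raises a safety concern. This is mandatory and is triggered by the report. Withdrawal for not following procedures is discretionary, and the only example given concerns attendance.
- **Stopping a session (5.2.3, repeated in 14.1).** "The subject may choose to discontinue stimulation at any time during the session if experiencing excessive discomfort or side effects".
- **Primary endpoint (3.1).** Besides recruitment feasibility, the study is to determine "if the intervention is well tolerated by smokers". No measure or threshold is given.
- **Adverse-event collection (5.2.3).** Adverse events are assessed by questionnaire before and after each session. The follow-up visit procedures in 5.2.4 list no adverse-event assessment.

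**The concern.** Tolerability is judged at least partly on what subjects say about their side effects. Under 13.1 one answer, a severity above moderate, ends participation. Under 12.3 ending participation early costs the bonus and all later visit payments. The two rules are reasonable separately, but together they put a price on candid reporting at the one severity level that matters most for a claim of good tolerability.

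Any distortion would run in the direction that favours the study's conclusion. An effect under-rated at a session has no planned second capture: 5.2.4 lists none, and the telephone contact in 13.2 covers smoking status and, for missed visits, whether and why the subject wishes to leave. The same wording could also make subjects hesitate to use the stop option, because they cannot tell from 12.3 whether using it costs them money.

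**Working it through.** **Inputs.** $20 per visit and a $60 bonus (12.3); one screening visit (5.2.1); two MRI visits for the scanned subgroup, "MRI scanning visits (2 visits, 1 visit occurring during the week prior to and the other visit occurring during the week following the tDCS visits") (5.2.2); five tDCS visits (5.2.3); four follow-up visits (5.2.4).

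**Step 1: reproduce the stated maximum.**
- Scanned: 1 + 2 + 5 + 4 = 12 visits; 12 × $20 + $60 = $300, matching 12.3.
- Not scanned: 1 + 5 + 4 = 10 visits; 10 × $20 + $60 = $260.

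**Step 2: the bonus as a share of the maximum.** $60 / $300 = 20% (scanned); $60 / $260 = 23% (not scanned).

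**Step 3: money forgone if withdrawn after a report at tDCS visit k.** Assume that day's visit is still paid; if not, add $20. Later visits: n = (5 − k) + 4 + m, where m = 1 if scanned and 0 otherwise. Later visit payments = $20 × n; total forgone = $20 × n + $60.

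| Subject | k | n | Later visit payments | Bonus | Total forgone |
|---|---|---|---|---|---|
| Scanned | 1 | 9 | $180 | $60 | $240 (80% of $300) |
| Scanned | 5 | 5 | $100 | $60 | $160 (53% of $300) |
| Not scanned | 1 | 8 | $160 | $60 | $220 (85% of $260) |
| Not scanned | 5 | 4 | $80 | $60 | $140 (54% of $260) |

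The later visit payments ($80 to $180) are for visits not made. The $60 is the part that depends on uninterrupted participation.

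**Step 4: stopping one session but staying in the study.** Three readings of 12.3 are possible:
- the stop is compliant and the visit is complete: $0;
- the stop is non-compliance but the visit is complete: $60;
- the stop is non-compliance and the visit is incomplete: $60 + $20 = $80.

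The text does not settle which applies.

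**Step 5: what remains if the bonus is protected.** The total falls by $60 in every row, for example from $240 to $180 (scanned, visit 1) and from $140 to $80 (not scanned, visit 5).

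**The case against.** The strongest reply is that no bias has been shown. The incentive works only if subjects know that a rating above moderate ends participation. Section 13.1 says they are told that taking part is voluntary; it does not say they are told the severity trigger. The consent form, which might explain the trigger or protect payment, is not in the text available for this review. This stands, and it limits the point to a risk of bias.

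Other parts also stand:
- Not paying for visits that do not take place is ordinary pro-rating, and payment already accrues visit by visit. A reader might take the full $140 to $240 as a penalty; only the $60 is a contingent reward for staying.
- A reader might infer that stopping a session forfeits the bonus. The documents do not say so. Stopping is expressly allowed in 5.2.3 and 14.1, so it may well count as compliant.
- A reader might infer that the incentive narrows the active–sham difference in side effects. The sham is not described, nothing says which arm produces more sensations, and section 16.0 specifies no between-arm tolerability comparison.
- A severe effect rated as moderate would still be recorded as an adverse event, and mild or moderate reports carry no stated loss unless they raise a safety concern.
- The missing definition of tolerability in 3.1 is the larger gap.

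These replies do not remove the core. Two stated rules combine so that a truthful severe rating costs the bonus, and no exemption appears. Defining tolerability would not cure this if the definition used the same reports.

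**Conclusion.** The point holds as a risk of bias in the tolerability part of the primary endpoint, towards looking well tolerated. A report above moderate severity makes the $60 bonus unattainable (20% or 23% of the maximum) and ends $80 to $180 of later visit payments if made during the tDCS week. Separately, 12.3 is ambiguous about stopped sessions, with a loss anywhere from $0 to $80.

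The conclusion assumes that subjects know, or come to learn, the withdrawal rule, and that the consent form contains no payment protection. The effect on an observed tolerability rate cannot be calculated: the documents give no expected rate, measure or threshold, and the planned figure of about 20 counts completers, which a subject withdrawn under 13.1 would not be. It would go beyond the text to say that the tolerability result is biased. This is a worthwhile, inexpensive correction, secondary to defining the tolerability endpoint.

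**What to change.** Amend 12.3 and the matching consent text to state that:

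- (a) attending a visit earns the $20 even if stimulation is stopped early;
- (b) stopping stimulation as 5.2.3 permits is not non-compliance for the purpose of the bonus;
- (c) a subject withdrawn under 13.1 for a side effect keeps the $60 bonus.

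Leave 13.1 as it is. The cost is a wording amendment and about $60 to $80 per affected subject. There is a small reverse incentive, because in these cases the bonus no longer requires full attendance. The change lowers the incentive to under-report but does not remove it, since payments for later visits still end on withdrawal.
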